2.2.2. Safety Analysis Set

Safety analyses will be performed on the safety population, which will be comprised of all randomized subjects who have been successfully dispensed a study lens.

2.3. Definition of Subgroups

Iris color information will be collected (Hue, and Lightness of iris) in order to categorize subjects into two groups “Dark” and “Light” iris to allow for comparisons within iris categories.

3. INTERIM ANALYSIS AND DATA MONITORING

There will be one planned interim analysis 6 weeks after first subject first visit. The interim analysis will include an analysis of Eyestrain score caused by glare. This study is the first time that data pertaining to Eyestrain will be collected. The analysis will be conducted when all dispensed subjects have completed

the 4-week follow-up evaluation. There are no pre-specified stopping rules planned in this interim analysis.

Adverse events, protocol deviations, and product complaints will be monitored throughout the study. For the purposes of this study the following definitions will apply:

Adverse Event: any untoward medical occurrence in a patient or clinical investigation subject administered a test article whether or not caused by the test article or treatment.

Protocol Deviation: any change, divergence, or departure from the study design or procedures of a research protocol that is under the investigator's control and that has not been approved by the IRB.

Product Complaint: any written, electronic, or oral communication that alleges deficiencies related to the identity, quality, durability, reliability, safety, effectiveness, or performance of a product after it is released for clinical trial use.

4. SUBJECT INFORMATION

4.1. Demographics and Baseline Characteristics

Demographic characteristics will be summarized by randomization and overall for all subjects enrolled using descriptive statistics for continuous variables, and numbers and percentages of subjects for categorical variables. Demographic information will include age, sex, and race.

4.2. Disposition Information

The disposition (accountability) of all enrolled subjects will be presented by study lens and overall to show the number and percentage of subjects in each of the following status subgroups:

1. Completed (Phase I): Subjects are considered to have completed Phase I of the study if they have completed all scheduled visits through Visit 6 (12-week Follow-up Visit).
2. Discontinued: Subjects are considered to have discontinued from the study if they are (i) randomized (ii) Successfully Dispensed and (iii) discontinued because of one of the following reasons: Unsatisfactory Lens Fitting due to study lens (a) Withdrew Consent (b) Lost to Follow Up (c) Subject no longer meets eligibility criteria (e.g. pregnancy) (d) Subject withdrawn by PI due to non-compliance to protocol (e) Discontinuation of study treatment as a result of the investigator's belief that for safety (f) Reasons it is in the best interest of the subject to stop treatment (g) Study lens no longer available (h) A scheduled visit was missed.
3. Total dispensed: Completed + Discontinued
4. Enrolled not Successfully Dispensed: Subjects are considered to be Enrolled Not Successfully Dispensed Subjects if they were (i) enrolled to the study (provided informed consent) but failed to satisfy the eligibility criteria (inclusion/exclusion criteria), (ii) were not randomized to study lens for any reason or (iii) if they are randomized but did not satisfactorily complete the dispensing process. This includes subjects who were dispensed a different type of study lens for each eye or who were dispensed same study lens for both eyes but did not return for any follow-up visits.
5. Total enrolled: Completed + Discontinued + Enrolled not Successfully Dispensed

The percentage will be calculated using total enrolled as denominator.

Safety and efficacy analysis sets will be defined as subsets of dispensed subjects (Completed + Discontinued).

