5	Lens Fit Assessment:	
The fit of the lens is judged by the investigator as pass or fail based on the criteria below. If the fit of the lens is judged as a failure, the subject is terminated from the study. To be judged as a failure, the lens must display one or more of the following:
 
 1. Limbal exposure in any gaze 2. Edge lift 3. Insufficient and/or excessive movement in all three movement categories 	
6	Lens Deposits	Record the front and back surface deposits of the lenses.	
7	Lens Wettability	Record the white light lens wettability of both lenses.	
8	Continuance	
For the subject to continue in the study, they must meet all three of the following criteria:
 
 1. Visual acuity is 0.17 logMAR (20/30) or better OD and OS 2. The lens fit is acceptable OD and OS 3. Investigator approval. If the investigator does not approve the dispensing of the first study lens, then the study is terminated for that subject. 	

VISIT 1: DISPENSING #1		Day 0
The following information will be collected:		
Steps	Details	
1	
Dispense
 
The lenses will be dispensed for 6-8 days.
 
 1. The subjects should wear their lenses similar to the inclusion criteria: ≥ 6 hours per day, ≥ 5 days per week. 2. The lenses will be worn as daily wear only. 3. All subjects will be provided Opti-Free PureMoist to be used in a rub regime. 4. Preservative-free rewetting drops are permitted if needed. 5. A patient instruction booklet will be provided. 6. The lenses must be stored in the supplied case out of direct sunlight. 
Note 1: In the event a lens is lost or damaged, the subject will return to the investigator site for replacement (extra lenses cannot be given at the dispensing visit).
 
Note 2: The subject's habitual contact lenses cannot be worn until during Visit 6 when they are placed back into their habitual lenses.
	
2	
Follow-up Visit Scheduling
 
An appointment for the next visit should be made for approximately 7 days (range 6-8 days) after Visit 1. Subjects should be advised to wear the study lenses at least 6 hours a day, and a minimum of 5 days per week. The study lenses must be worn into the Follow-up Visit.
	

VISIT 2: 7-DAY FOLLOW-UP		(Follow-up #1, 6-8 days after Visit 1)
The following information will be collected:		
Steps	Details	

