5.1 WITHDRAWAL CRITERIA

A subject may be withdrawn from the study for any of the following reasons:

- Lost to follow-up
- Withdrawal of consent
- Death

- Subject was randomized but did not satisfactorily complete the fitting process,
- A scheduled visit is missed,
- Subject no longer met eligibility criteria (i.e. subject became pregnant during the study),
- Discontinuation of study treatment as a result of the investigator's belief that for safety reasons (e.g., adverse event) it is in the best interest of the subject to stop treatment.
- Non-compliance to the protocol.

For discontinued subjects, the Investigator will:

- Update the enrollment log to document reason for discontinuation and provide to CRA
- Complete the "last" Follow-up Visit form (scheduled or unscheduled)
- Complete the Final Evaluation form, indicating the reason that the subject was discontinued from the study
- Record the spherocylindrical refraction with best corrected distance visual acuity
- Collect used study lenses and test articles (worn or brought to the visit) from the subject and discard them
- Collect all unused study lenses and test articles from the subject

Subjects becoming pregnant during the study will be discontinued. Once discontinued, pregnant participants and their fetuses will not be monitored for study related purposes. At the Investigators' discretion, the study participant may be followed by the Investigator through delivery. However, this data will not be collected as part of the clinical study database. Pregnant participants are not discontinued from contact lens or solution related studies for safety concerns, but due to general concerns relating to pregnancy and contact lens use. Specifically, pregnant women are discontinued due to fluctuations in refractive error and/or visual acuity that occur secondary to systemic hormonal changes, and not due to unforeseen health risks to the mother or fetus.

Investigators may be asked to replace discontinued subjects if the minimum target number of total subjects across all sites may otherwise not be met.

In cases where a subject is lost to follow-up, every possible effort must be made to contact the subject and determine the reason for discontinuation / withdrawal. The measures taken to follow up must be documented including two written attempts and a certified letter as the final attempt.

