8.1 SAFETY PARAMETERS

All subjects randomized and treated will be in the safety analyses. All reported AEs will be summarized. All safety data will be listed by subject. The following safety parameters will be monitored and evaluated:

- Adverse events
- Ocular physiology (corneal staining, limbal and bulbar conjunctival redness)
- Ocular symptoms
- Slit Lamp Findings
- Lens Deposits
- Reasons for discontinuation

- Lens damage
- Reason for unplanned lens replacement
- Snellen VA

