8.4 METHODS FOR ASSESSING, RECORDING AND ANALYZING SAFETY

The recording and documenting of adverse events (ocular and non-ocular) begin when the subjects are exposed to the test article or study treatment. Adverse events reported before the use of test article or start of study treatment should be recorded as medical history. Untoward medical events reported after the subject's exit from the study will be recorded as adverse events at the discretion of the Investigator.

All adverse events observed by the Investigator; reported by the subject spontaneously; or in response to direct questioning; will be recorded in the source document. Such documentation will include a description of the adverse event, time of onset, duration of event, treatment regimen instituted, any referral to another health care provider (if needed), any new concomitant medications, outcome, ocular damage (if any), and likely etiology. Best Corrected Visual Acuity (BCVA) should be recorded prior to the report of an adverse event (as part of the baseline evaluation), upon report of the subject's report of the adverse event, and after the adverse event has resolved. All adverse events will be followed in accordance with licensing requirements.

All adverse events will be documented in the appropriate section of the subject's Case Report Form (CRF). In conjunction with the medical monitor, the Investigator will evaluate adverse events to ensure the events are categorized correctly. Elements of categorization will include:

- Seriousness (see definition in Section 8.3)
- Expectedness – i.e. if the event was unexpected or unanticipated in that it was not previously identified in nature, severity, or degree of incidence (see definition in Section 8.3)
- Causality or Relatedness – i.e. the relationship between the test article and the adverse event (not related; doubtful; possible; probable; very likely - see definition in Section 8.3)
- Adverse Event Intensity or Classification – Adverse event intensity is used to assess the degree of intensity of the adverse event (mild, moderate, severe for all events). In addition Adverse event Classification is used to assess the severity of ocular adverse events (AE not requiring treatment, non-significant or significant see definition in Section 8.3).
- Outcome – Fatal, not resolved, resolved, resolved with sequelae, resolving and unknown.
- Actions Taken – None, temporarily discontinued, permanently discontinued
- Other action taken

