9.7 EVALUABLE SUBJECTS

Subjects will be allocated to one of four mutually exclusive groups:

1. Enrolled, Not Randomized: Subjects are considered to be Enrolled Not Randomized if they were (i) enrolled to the study (provided informed consent) but failed to satisfy the eligibility criteria (inclusion/exclusion criteria) or (ii) were not randomized to study lens for any reason.
2. Randomized, Not Successfully Dispensed: Subjects are considered to be Randomized Not Successfully Dispensed if they are randomized but did not satisfactorily complete the dispensing process. This includes subjects who were dispensed a different type of study lens for each eye or who were dispensed same study lens for both eyes but did not return for any follow-up visits.

3. Successfully Dispensed, Discontinued Subjects: Subjects are considered to have discontinued from the study if they are (i) randomized (ii) Successfully Dispensed and (iii) discontinued because of one of the reasons described in section 5.1.
4. Successfully Dispensed, Completed Subjects: Subjects are considered to have completed the study if they have completed all required visits through Visit 8 (14-week Follow-up Visit).

Safety and efficacy analysis sets will be defined as subsets of successfully dispensed subjects (completed + discontinued).

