1. INTRODUCTION

1.1. Background

This document describes the data analysis specifications for protocol CR-5638 titled “Long-term Evaluation of [REDACTED] UV Blocker”. The test article is the J JVCI Investigational Contact Lens [REDACTED] while the control is ACUVUE® OASYS®. This study is 2- Phase randomized, 8-visit, partially subject-masked (Control arm only), 14-week dispensing trial. The study lenses will be worn as daily wear (DW) for a period of 12 weeks, with follow-up visits occurring after 1-, 2-, 4-, 8- and 12-weeks. All visits up to visit 6 are considered to be Phase I of the study while visits 7 and 8 are considered to be Phase II of the study. After the 12-week follow-up has occurred (Phase I has completed); the habitual lenses will be worn for a period of two weeks with weekly visits (Phase II).

The document is intended to describe the guidance for statistical analysis up to the 12-week follow up (Phase 1) and will supersede section 9 in the protocol if there are any discrepancies (i.e. See Amendment History section)

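### Dispensed subjects who never return fall outside the safety set, against Protocol 8.1, and an unscheduled-visit event with no later visit has no stated place in the safety model (small effect, wording fix)

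*SAP*

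**What the plan says.** **Safety set.** Protocol 8.1 states: "All subjects randomized and treated will be in the safety analyses". SAP 2.2.2 describes the set as "all randomized subjects who have been successfully dispensed a study lens", and Protocol 9.1 is similar. The qualifier about successful dispensing gets its meaning in the disposition rules. SAP 4.2 puts into the not-successfully-dispensed class subjects who "were dispensed same study lens for both eyes but did not return for any follow-up visits". It then limits both the safety and efficacy sets to completed plus discontinued subjects. Protocol 9.7 does the same. On precedence, SAP 1.1 says that the SAP "will supersede section 9 in the protocol if there are any discrepancies".

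**Unscheduled visits.** SAP 6.2.1, SAP 6.2.2 and Protocol 9.1 count a slit-lamp event found at an unscheduled visit at the scheduled visit that follows. For symptoms, SAP 6.2.1 says the subsequent visit. The example given places an event between Visits 1 and 2 in Visit 2. No text covers a subject for whom no later visit takes place. The synopsis (Protocol 1.8) excludes unscheduled visits from the analysis in general, whereas Protocol 9.1 excludes them from the efficacy analysis only.

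**The concern.** A safety set should contain everyone exposed to the product. Here a person can take study lenses home, wear them, and be removed from the safety denominator for not coming back. Safety information on such a person can exist: adverse-event recording is to "begin when the subjects are exposed to the test article or study treatment" (Protocol 8.4), and for those lost to follow-up "every possible effort must be made to contact the subject and determine the reason for discontinuation / withdrawal" (Protocol 5.1).

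The second gap concerns the comparison between arms. The plan foresees subjects whose last contact is an unscheduled visit: Protocol 5.1 and SAP 4.2 make a missed scheduled visit a reason for discontinuation, and Protocol 5.1 allows the last follow-up form to be an unscheduled one. Protocol 8.3 lists grade 3 or higher corneal findings in a class of events described as usually leading to temporary or permanent lens discontinuation. The event that defines the primary safety endpoint can therefore be the reason why its own time point never occurs. A loss of that kind depends on outcome and is not random.

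**Working it through.** **Part 1: who is in the set**

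| Text | Rule | Dispensed, never returned |
|---|---|---|
| Protocol 8.1 | randomized and treated | in |
| Protocol 9.1, SAP 2.2.2 | randomized and successfully dispensed | depends on disposition class |
| Protocol 9.7, SAP 4.2 | never-returners not successfully dispensed; set = completed + discontinued | out |

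Protocol 8.1 is in section 8, which the SAP does not claim to override. Protocol 9.7 agrees with the SAP, so the Protocol also contradicts itself.

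The plan's only counts near this topic are the historical ones in SAP 1.5. Enrolled: 89 + 71 + 109 = 269. Not dispensed: 1 + 2 + 3 = 6. Dispensed: 269 − 6 = 263, as stated. Completed 84 + 67 + 100 = 251 plus discontinued 4 + 2 + 6 = 12 also gives 263.

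The number of never-returners per arm, k, is not given and is assumed here. The top value, 10, uses the whole planned allowance from 60 enrolled to 50 completed. To show the denominator effect, take the exact 95% upper limit for zero events, 1 − 0.025^(1/n). The SAP does not plan this interval.

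| k | n | Upper limit for 0/n |
|---|---|---|
| 0 | 60 | 6.0% |
| 1 | 59 | 6.1% |
| 3 | 57 | 6.3% |
| 5 | 55 | 6.5% |
| 10 | 50 | 7.1% |

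A single adverse event in a single never-returner is 1/60 = 1.7% if that person is included; if excluded, the arm shows 0/59.

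**Part 2: unscheduled-visit events**

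*Grade 3 or higher.* SAP 1.5 anticipates at most 0.5% of eyes. At that ceiling, 120 × 0.005 = 0.6 eyes per arm. The chance of exactly one event in an arm is 33% (120 independent eyes), 22% (60 subjects) or 15% (600 eye-visits). Suppose one Control event at week 4, and one Test event at an unscheduled visit before Visit 2 in a subject who then leaves. Control has 60 × 2 × 5 = 600 rows. Test has 59 × 10 = 590 rows, or 592 if the unscheduled visit supplies the Visit 2 row for both eyes.
- Assigned: 8 of the 10 group-by-visit cells are empty. Unassigned: 9 of 10 are empty. The group*time model gives no finite estimates in either case.
- Reduced model, assigned: (1/591)/(1/599) = 1.01, 95% CI 0.06 to 16.2. Unassigned: 0/590 v 1/600, so no finite odds ratio.

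*Grade 2 or higher fallback.* SAP Table 1 gives Test 3/154 and 5/150, Control 30/102 and 23/100, with no grade 3 or higher findings. For 120 Test eyes that is 120 × 3/154 = 2.34 and 120 × 5/150 = 4.0. Control odds are 30/72 = 0.417 and 23/77 = 0.299.
- Week 1: (2.34/117.66)/0.417 = 0.05; with one more Test eye, (3.34/116.66)/0.417 = 0.07.
- Week 2: (4/116)/0.299 = 0.12; with one more, (5/115)/0.299 = 0.15.

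*Symptoms.* Assumed: b of 60 Control subjects report symptoms at each of five visits; Test subjects who stay have the same rate; L further Test subjects report symptoms at an unscheduled visit before Visit 2 and leave; both eyes alike; no Control leavers. The crude pooled counts are then:
- Control: 5b of 300.
- Test, assigned: 5(60 − L)b/60 + L, of 5(60 − L) + L.
- b = 12, L = 1: 60/296 v 60/300, OR = (60/236)/(60/240) = 1.02.
- b = 6, L = 2: 31/292 v 30/300, OR = (31/261)/(30/270) = 1.07.
- b = 3, L = 3: 17.25/288 v 15/300, OR = (17.25/270.75)/(15/285) = 1.21.
- Unassigned: the rates are equal, OR = 1.00.

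If the arms are instead given equal symptom counts among those who stay, the ranges are 1.04–1.27 assigned and 1.02–1.07 unassigned.

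*Why negative results must also enter.* Take three Test leavers, one positive, and 6 events among the other 57. No leavers counted: 6/57 = 10.5%. Positives only: 7/58 = 12.1%. All counted: 7/60 = 11.7%. Admitting positives alone overstates the rate.

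**The case against.** The other side has good arguments, and most of them limit the size of the point.

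- **The intent is visible.** SAP 6.2.1 says that the safety endpoints are evaluated during unscheduled visits as well, and its example is an assignment by interval. That is probably what the authors meant, and loss of the event is only one literal reading. But the example involves a Visit 2 that is held. Two programmers could code the other case differently.
- **Nothing disappears from the report.** SAP 6.3 lists all reported adverse events, and Protocol 9.1 summarizes unscheduled visits separately. This stands. What can be lost is a place in the denominators, the summaries and the between-arm comparison.
- **The never-return group is narrow.** Protocol 4.4 and SAP 1.3 speak of unscheduled follow-up visits, so a subject seen only at one arguably did return. That would leave people with no examination after dispensing, and Part 1 would then cost no slit-lamp data. The documents do not settle this.
- **The study is exploratory.** Protocol 3.1 and SAP 1.4 say so, and no decision rests on a reduced-model odds ratio with an interval from 0.06 to 16.2. This also stands. SAP 6.2.2 allows further analyses by subject or visit if needed, but leaves them unspecified.

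**Conclusion.** Both parts hold, as minor points. Part 1 is a stated rule that contradicts Protocol 8.1 and removes treated people. Part 2 is a missing rule whose literal reading loses events in a way related to outcome. Neither changes the planned sample size, power or significance level. The Part 1 figures rest on an assumed number of never-returners. The Part 2 symptom figures rest on assumed rates with every leaver symptomatic and in the Test arm.

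Four stronger inferences are not supported:

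- A reader might size Part 1 from the 12 of 263 historical subjects who discontinued. Under this plan's definitions, discontinued subjects are successfully dispensed and never-returners are not. If the historical studies used the same convention, never-returners would be among the 6 not dispensed. The documents do not say, so 12/263 neither bounds nor estimates the number.
- A reader might expect a marked shift in symptom odds ratios at week 1. SAP 6.2.2 compares arms at each visit only if the lens-by-time interaction is significant at 15%. The ordinary planned output is the pooled odds ratio.
- A reader might note that one eye is a large share of two to four Test eyes with grade 2 or higher findings. If the Table 1 rates hold, the Test v Control comparison barely moves.
- A reader might extend Part 1 to subjects stopped at the Visit 1 fitting ("If the fit of the lens is judged as a failure, the subject is terminated from the study", Protocol 4.7.1). They are not dispensed lenses, and no passage says whether a lens tried on in the clinic makes a subject treated under Protocol 8.1. The documents do not decide that case.

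**What to change.** 1. In SAP 2.2.2, define the safety set as all randomized subjects dispensed at least one study lens, whether or not they returned. Keep never returned as a disposition row only. Reconcile Protocol 8.1, 9.1 and 9.7 with SAP 2.2.2 and 4.2.
2. In SAP 6.2.1 and 6.2.2, state that slit-lamp and symptom events from unscheduled visits are assigned to the next planned visit interval, whether or not that visit is held. Where it is not held, let the unscheduled result, positive or negative, supply the row.
3. Align the synopsis with Protocol 9.1, so that unscheduled visits are excluded from the efficacy analysis only.

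The cost is SAP and protocol wording plus one programming rule. No new data are needed. Protocol 6.3 already requires slit-lamp findings at unscheduled visits for device-related problems, and the schedule of events in Protocol 4.4.1 marks symptoms there.
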